6.3 Safety and Other Assessments

The following safety assessments will be performed by appropriately trained staff/clinical examiners, at the times and in the order defined in the **STUDY PROCEDURES** section of this protocol.

6.3.1 OST Examination

This procedure will be conducted by a qualified, experienced clinical examiner. The OST examination will be accomplished by direct observation and palpation with retraction aids, as appropriate. The examination will cover the oral labial mucosa (including lips), buccal mucosa, mucogingival folds, gingival mucosa, hard palate, soft palate, tonsillar area, pharyngeal area, tongue, sublingual area, submandibular area and salivary glands. Findings from the examination will be recorded in the CRF as either normal or abnormal, with details of any abnormalities. The results of the OST examination performed at screening will be used to determine subject eligibility. Any new OST abnormality or worsening of a pre-existing condition observed by the clinical examiner or reported by the subject after the screening examination will be recorded as an AE.

Where possible, this procedure should be conducted by a single clinical examiner.

6.3.2 OHT Examination

This procedure should be conducted by a qualified, experienced clinical examiner. The OHT examination will be accomplished by direct observation, using retraction aids as appropriate and will identify any grossly carious lesions, signs of erosive wear, enamel irregularities, tooth fracture, gross generalized dental caries decay, decalcification and faulty restorations. The presence of any implants, fixed or removable dentures, fixed or removable orthodontic braces/bands, fixed orthodontic retainers, full crowns or veneers will be recorded. Observations will be listed as either absent or present, and conditions noted as present will be described in the CRF. Any change observed by the clinical examiner or reported by the subject after the screening examination will be recorded as an AE.

The results of the OHT examination performed at Screening will be used to determine subject eligibility.

Where possible, this procedure should be conducted by a single clinical examiner.

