Within 14-28 days of Screening (Visit 1), eligible subjects will return to the site for the Baseline visit (Visit 2) with overnight plaque (subjects will be instructed to abstain from oral hygiene for 12 hours [+6 hours; -2 hours] i.e., overnight immediately before the visit).

At the Baseline visit, subjects will undergo, in the following order, a full OST examination, assessments of gingival inflammation (MGI), gingival bleeding (EBI), and supra-gingival plaque (TPI). Subjects with % bleeding sites (derived from EBI assessment) and TPI score outside the study range will be discontinued from the study at this visit. Eligible subjects will then receive full mouth dental prophylaxis and be randomized to study product. The dental prophylaxis (followed by flossing) is to remove sub and supra-gingival calculus, stain, plaque and debris from the teeth. All subjects will enter the treatment period with no visible plaque (TPI=0).

Subjects will then undergo a supervised product use. Subjects will be instructed to use their product twice daily, per instruction, until their next visit.

After using the study product(s) for 6, and 12 weeks, subjects will return to the study site (Visits 3 and 4, respectively) with overnight plaque (subjects will be instructed to abstain from overnight toothbrushing for 12 hours [+6 hours; -2 hours] immediately before each assessment visit), at approximately the same time of day as the Baseline visit. The study product use will be reviewed to determine treatment compliance. During the visit 3 and 4, the investigator will ask subjects about product usage compliance and remind them to follow product usage instructions (visit 3 only). The investigator will also ask subjects if there are any changes in their health and medical occurrences since the last visit. Subjects will have a full OST examination and then undergo, in the following order, MGI, EBI, and TPI assessments. At Visit 4, subjects will also have a full OHT examination, return all study supplies if required and have a dental prophylaxis if deemed appropriate by the investigator or examiner.

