8.3.3 Safety Analysis(es)

Safety analyses will be performed on the Safety population, according to investigational product received. AEs will be regarded as ‘treatment emergent’ if they occur on or after the first use of investigational product at Baseline. In the event of a missing start date, an AE will be assumed to be ‘treatment emergent’ unless the end date is prior to starting treatment. In case of misallocation, compared to the randomization schedule, TEAEs will be associated with the most recent study investigational received.

Each AE will be categorized as oral or non-oral by the investigator or medically qualified designee. All will be reviewed by the CRS and coded using the MedDRA prior to database lock and unblinding.

A listing of all AEs will be presented for all subjects in the Safety population with the following AE summaries (number of distinct AEs and frequency/proportion of subjects affected) presented by treatment group and overall:

- TEAEs
- TEAEs by System Organ Class (SOC) and Preferred Term (PT)
- TEAEs by Oral/Non-Oral and PT
- Treatment emergent treatment related AEs by Oral/Non-Oral and PT
- Treatment emergent treatment related serious AEs by SOC and PT

Separate listings will be presented for:

- Deaths, SAEs and any AEs leading to product or study discontinuation.
- OST findings (with a summary of abnormalities by visit)

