9.2 Definition of an AE

An AE is any untoward medical occurrence in a clinical study subject, temporally associated with the use of a study product including any washout or lead-in product (or medical device), whether or not considered related to the study product, including any washout or lead-in product (or medical device).

NOTE: An AE can therefore be any unfavorable and unintended sign (including an abnormal laboratory finding), symptom, or disease (new or exacerbated) temporally associated with the use of a study product including any washout or lead-in product (or medical device).

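### The hard-tissue rule records a change in either direction as an AE, and a change of unknown onset first seen at Week 12 defaults to treatment emergent

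*Protocol*

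**What the plan says.** **The hard-tissue rule.** Protocol 6.3.2 states: "Any change observed by the clinical examiner or reported by the subject after the screening examination will be recorded as an AE". The findings it covers are scored as absent or present and include faulty restorations. The same section also captures dental work: "full crowns or veneers will be recorded".

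**The neighbouring texts.** For soft tissue, Protocol 6.3.1 limits AE recording to "Any new OST abnormality or worsening of a pre-existing condition observed by the clinical examiner or reported by the subject after the screening examination". Protocol 9.2 gives the general definition: "An AE is any untoward medical occurrence in a clinical study subject, temporally associated with the use of a study product".

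**When hard tissue is examined.** The schedule of activities (Protocol Table 5-1) puts OHT at Screening and Visit 4 only. The study design section agrees. For Baseline it says "At the Baseline visit, subjects will undergo, in the following order, a full OST examination", with no hard-tissue counterpart, and for Week 12 it says "At Visit 4, subjects will also have a full OHT examination".

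**How events become TEAEs.** Protocol 8.3.3 counts AEs from first product use at Baseline onwards. It adds a default for undated events, in which the closing words refer to the start of study product: "In the event of a missing start date, an AE will be assumed to be ‘treatment emergent’ unless the end date is prior to starting". SAP 4.5.1 uses the same starting point and classes an earlier onset as non-treatment emergent. It has no rule for a missing AE onset date; its missing-date clause concerns the date of first product use. SAP Table 5-1 lists no change from the protocol on this point.

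**The concern.** TEAEs over 12 weeks are the only safety endpoint, and the SAP gives oral TEAEs a table split (14.3.1.3) and a listing (14.3.2.4). The SAP plans no by-product summary of OHT findings, only a listing of conditions present, so a hard-tissue change reaches the summary tables only through the AE form.

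Two features of the plan affect what those tables mean.

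- **Direction.** A rule that counts any change also counts a defect that has gone or a tooth that has been restored. That does not fit an AE definition built on untoward occurrences, nor the soft-tissue rule in the section just before it.
- **Timing.** No hard-tissue examination is scheduled at first product use. A change first seen at Week 12 may have arisen on product or during the washout on a different toothpaste, and the examination alone cannot tell which. If onset is unknown, the protocol's default places it on product.

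At stake is whether an oral TEAE count drawn partly from OHT findings represents adverse changes arising on study product.

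**Working it through.** The plan states no figure on this point, so there is none to reproduce. The check compares the rules and then measures the interval.

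**1. The same findings under the three rules**

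| Finding, Screening to Week 12 | 6.3.2 read literally | 6.3.1 rule carried over to OHT | 9.2 |
|---|---|---|---|
| Defect absent, then present | AE | AE | AE if untoward |
| Defect present, then worse | AE | AE | AE if untoward |
| Faulty restoration present, then repaired | AE | not an AE | repair is not untoward |
| Full crown absent, then placed | AE | not an AE in itself | placement is not untoward in itself |

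The rules part on the last two rows. The event that led to a repair may be a genuine AE, but the repair is not. Such cases remain possible: Protocol 4.4.3 defers non-emergency dental treatment but allows for emergency treatment, and exclusion 20e removes only subjects with numerous poor restorations.

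**2. Which changes can be misdated**

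- Onset known to precede first product use: non-treatment emergent (SAP 4.5.1). Correct.
- Onset known to follow first product use: treatment emergent. Correct.
- Onset unknown: treatment emergent by default (Protocol 8.3.3). Possibly wrong.
- Onset entered as the date of the Week 12 examination: treatment emergent. Possibly wrong. Neither document says how to date a change first seen at that examination.

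Only the last two groups are exposed.

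**3. How much of the interval precedes product use**

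Inputs: Screening to Baseline, w = 14 to 28 days (Protocol 5.3); Baseline to Week 12, v = 84 ± 4 days, so 80 to 88 (Protocol 5.5).

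Interval between the two OHT examinations = w + v, from 14 + 80 = 94 to 28 + 88 = 116 days.

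Pre-product share = w / (w + v):

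- nominal Day 84: 14/98 = 14.3% to 28/112 = 25.0%
- with the visit window: 14/102 = 13.7% to 28/108 = 25.9%

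Under a constant rate of change, with every washout change left undated, this would be the share of OHT-derived TEAEs that predate product. The excess over the true on-product count would then be w / v, or 14/84 = 16.7% to 28/84 = 33.3%. Each washout change that is noticed and dated at Baseline lowers both figures, so under a constant rate they are ceilings. The documents give no OHT event rate from which to estimate a number of events.

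**The case against.** The best defence is that the AE definition already does the filtering. Protocol 9.1 asks staff to report events that meet that definition, 9.2 requires something untoward, and 9.5.1 requires an intensity grade, which a repair or a resolved defect cannot sensibly be given. Most of the OHT list consists of defects, so a change could be read as a new defect. The eCRF captures only conditions present (SAP Table 5-1), so a defect gone by Week 12 leaves no positive OHT entry then. These points make a literal application less likely. They do not remove the conflict: 6.3.2 is an unqualified instruction, and nothing subordinates it to 9.2.

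The missing-date default is a deliberate conservative choice, and a sound one. It should stay.

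Several stronger readings are tempting, and the documents do not support them.

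- **A reader might infer that pre-product changes in general are counted as TEAEs.** They are not. SAP 4.5.1 excludes known earlier onset, and AEs are collected from consent and at each visit. At Visit 2 the teeth are scored, cleaned and checked by a second clinician, which gives a further chance to notice a change, although it is not an OHT examination.
- **A reader might take 14% to 25% as the proportion of TEAEs misclassified.** It is a share of time and applies only to OHT-derived events, not to oral TEAEs as a whole.
- **A reader might infer that real differences between arms are diluted.** Equal background counts leave the expected absolute difference unchanged; only ratios shrink. The planned TEAE summaries are descriptive, with no between-arm test.
- **A reader might want defects uncovered by the Baseline prophylaxis excluded automatically.** Without an OHT record after prophylaxis that attribution cannot be verified, and the exclusion could suppress real decalcification or wear. Subjects with high stain or calculus that could interfere with plaque assessments are already excluded (20i).

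**Conclusion.** The point holds as a minor one about safety reporting, in two parts.

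- **Direction:** Protocol 6.3.2 conflicts with 9.2 and with 6.3.1. Read literally, it makes improvements and repairs AEs that can enter the TEAE tables. This rests on the wording alone and needs no assumed rate.
- **Timing:** only a change first seen at Week 12, with onset unknown or set to the date of discovery, can be wrongly placed on product. The pre-product part is 14 to 28 days, about 14% to 25% of the interval at nominal Day 84. As a share of events this is an upper bound that assumes a constant rate and no washout change dated at Baseline.

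The documents do not allow a number of affected events to be given. It is likely to be small, because elective dental treatment is deferred and AEs are collected throughout. The rule is identical in all three arms, and the primary endpoint, overall number of bleeding sites at Week 12, is unaffected.

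**What to change.** **Protocol 6.3.2.** Replace the any-change rule with the 6.3.1 formula carried over to hard tissue, so that only a new OHT abnormality, or the worsening of one already there, is recorded as an AE. The model is the sponsor's own: "Any new OST abnormality or worsening of a pre-existing condition observed by the clinical examiner". This also brings 6.3.2 into line with 9.2.

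**SAP 4.5.1.** For each OHT-derived AE first found at Week 12, have the investigator record onset as before, after or unknown relative to first product use. Carry over the conservative default from Protocol 8.3.3, so that unknown onset still counts as treatment emergent. Show events of unknown onset on a separate row of Table 14.3.1.3, or footnote them.

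**Cost.** One protocol sentence, one SAP sentence, one table row or footnote, and one extra investigator judgement per affected finding. The reported oral TEAE count may fall slightly. No added visit or examination is needed.

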6.3.3 Pregnancy Testing

For this study, the products being tested are not contra-indicated for pregnancy or intended to be contra-indicated for pregnancy and use of them would not be expected to cause harm either to the mother or fetus. **A pregnancy test is therefore not required.** However, subjects of child-bearing potential will be asked to provide verbal confirmation of pregnancy status at screening (Visit 1) and at each subsequent study visit. Subjects will be instructed to inform site staff if they find they are pregnant while participating in the study. In case of a positive confirmed pregnancy, the subject will be withdrawn from the study.

[figure not shown]
6.3.4 Exit Satisfaction Survey

At the end of the study (Visit 4), subjects in toothpaste/mouthwash treatment arm will be asked to rate their level of satisfaction with the toothpaste and the mouthwash using a Numeric Rating Scale (NRS).

The NRS is an 11-point ordinal scale used to assess the subject's satisfaction with the toothpaste and mouthwash. The scale ranges from 0 (completely dissatisfied) to 10 (completely satisfied), with higher scores indicative of greater satisfaction ([van Berckel et al., 2017](#)):

see example below.

Subjects will be asked to record the numeric value on the segmented scale that best describes their level of satisfaction after 12 weeks twice daily use and indicate why they select a particular score in answer to the question 'Please give more details on why you are satisfied or dissatisfied with the product' (free text response).

Example NRS - Not to Scale

In addition, subjects will be asked whether they would recommend this product to their family and friends who have gum problems. The responses will be either “yes” or “no” followed by free text describing why the choice is made.

An example of a satisfaction survey questionnaire is included in section 10.2.

Property of Haleon- Confidential

May not be used, divulged, published or otherwise disclosed without the consent of Haleon

CCI Abbreviated Clinical Protocol Template v1.0

To ensure the examiner remains blinded throughout the study, subjects will complete the exit satisfaction survey in a separate area.

7 INVESTIGATIONAL/STUDY PRODUCTS

For the purposes of this study, per International Conference on Harmonization (ICH) guidelines, and Haleon policy, study intervention is defined as any investigational intervention(s), marketed product(s), placebo, or medical device(s) intended to be administered to a study participant according to the study protocol.

This includes a product with a marketing authorization when used or assembled (formulated or packaged) in a way different from the approved form, or when used for an unapproved indication, or when used to gain further information about an approved use.

7.1 Investigational/Study Product Supplies

The following study products will be supplied by the Clinical Supplies Department, Haleon:

Table 7-1 Investigational/Study Product Supplies

	Test Products (Toothpaste/Mouthwash)	Reference product (Negative control, toothpaste)	Reference product (Toothpaste)
Product Name	parodontax Complete Protection Toothpaste (0.454% w/w SnF ₂) + parodontax Active Gum Health Mouthwash (0.07% w/w CPC)	Crest Cavity Protection (0.243% w/w sodium fluoride)	parodontax Complete Protection (0.454% w/w SnF ₂)
Pack Design	Carton of 6 over-wrapped tubes (toothpaste) + 12 blinded bottles (mouthwash)	Carton of 6 over-wrapped tubes	Carton of 6 over-wrapped tubes
Dispensing Details	One carton (toothpaste) – baseline visit + 6 blinded bottles (mouthwash) – baseline visit	One carton – baseline visit	One carton – baseline visit

Property of Haleon- Confidential

May not be used, divulged, published or otherwise disclosed without the consent of Haleon

CCI

Abbreviated Clinical Protocol Template v1.0

Haleon

Clinical Protocol

Protocol Number: 300211

HALEON

	6 blinded bottles (mouthwash) – week 6 visit		
Product Master Formulation Code (MFC)	Toothpaste CCI (US Commercial Product) Mouthwash CCI (US Commercial Product)	US Commercial Product	CCI (US Commercial Product)
Dose/Application	Toothpaste: Full ribbon of toothpaste on head of toothbrush provided Mouthwash: 20 milliliters of mouthwash	Full ribbon of toothpaste on head of toothbrush provided	Full ribbon of toothpaste on head of toothbrush provided
Route of Administration	Oral, Topical	Oral, Topical	Oral, Topical
Usage Instructions	Subjects will brush their teeth for at least one (timed) minute twice a day (morning and evening). After each brushing (morning and evening), subject will swish 20 milliliters of the mouthwash vigorously between teeth for 30 seconds. No further rinsing with water is permitted.	Subjects will brush their teeth for at least one (timed) minute twice a day (morning and evening)	Subjects will brush their teeth for at least one (timed) minute twice a day (morning and evening)
Return Requirements	All used/unused samples to be returned	All used/unused samples to be returned	All used/unused samples to be returned

Property of Haleon- Confidential

May not be used, divulged, published or otherwise disclosed without the consent of Haleon

CCI Abbreviated Clinical Protocol Template v1.0

Haleon
Clinical Protocol
Protocol Number: 300211

HALEON

Table 7-2 Washout/Acclimatization/Lead-in Product Supplies

	Washout toothpaste
Product Name	Colgate Cavity Protection
Pack Design	Labelled commercial tube
Dispensing Details	One tube – screening visit
Product Master Formulation Code (MFC)	N/A - commercial product
Dose/Application	Apply a full ribbon of toothpaste on the head of toothbrush provided
Route of Administration	Topical oral use
Usage Instructions	Subjects will brush their teeth according to their normal brushing habits twice a day (morning and evening).
Return Requirements	All used/unused samples to be returned

Table 7-3 Sundry Items

Sundry Items to be supplied:

Item	Supplied By	Pack Design	Dispensing Details	Return/Disposal Details	
				Used Samples	Unused Samples
Sensodyne Sensitive Care soft-bristled Toothbrushes (US marketplace)	Haleon	Commercial pack (2 brushes/pack)	1 brush at screening visit 1 brush at baseline visit	Destroy at site using site disposal procedures	Return not required
Countdown Timer	Haleon	Individual commercial pack – 1 per subject	Baseline visit	Subject to keep or destroy at site using site	Return not required

Property of Haleon- Confidential

May not be used, divulged, published or otherwise disclosed without the consent of Haleon

CCI Abbreviated Clinical Protocol Template v1.0

Haleon

Clinical Protocol

Protocol Number: 300211

HALEON

				disposal procedures	
Opaque Bags	Haleon	Commercial Pack	Screening Visit, baseline visit & week 6 visit (toothpaste/mouthwash group)	Subject to keep or destroy at site using site disposal procedure	Return not required
Dosing cups for mouthwash home use (toothpaste/mouthwash group)	Haleon	Commercial Pack	6 cups at Baseline visit 6 cups at week 6 visit	Subject to keep or destroy at site using site disposal procedure	Return not required
Acclean Disclosing Solution	Haleon	Commercial Pack	Baseline, week 6 and 12	Destroy at site using site disposal procedure	Return not required

7.2 Product Supplies Product Storage, Accountability, Returns and Destruction

All study products supplied are for use only in this clinical study and should not be used for any other purpose.

Guidance will be provided to the Investigator and site staff for the receipt, storage and management of products for the duration of the trial by Haleon Clinical Supplies during the Site Initiation Visit and with further instructions included with the shipping documentation.

The site should ensure that the room or area set aside for storage is able to maintain the correct temperature to meet the product label storage conditions, is sufficient to store all products and is secure and access controlled.

Any temperature excursions or discrepancies during transit or whilst study products are stored at site require the affected products to be quarantined and this must be communicated immediately to the Sponsor who will provide documentation to approve further usage.

Use of any of the affected product(s) prior to sponsor approval will be considered a protocol deviation.

Study products are to be dispensed only to subjects enrolled in the study in accordance with the protocol, by authorized site staff. Subjects will be informed on product usage, storage, return and what to do in the event of product loss when they are first dispensed after enrolment. Returned study products should not be re-dispensed to any subject.

Property of Haleon- Confidential

May not be used, divulged, published or otherwise disclosed without the consent of Haleon

CCI Abbreviated Clinical Protocol Template v1.0

All study products will be accounted for using the investigational/study product accountability form/record. The Investigator is responsible for study product accountability, reconciliation, and record maintenance.

Detailed instructions for the return of study product/study supplies will be provided by Haleon during the study in time for study close out. Investigational products can only be destroyed at site in agreement with and after approval from the Sponsor.

